### 7.2 Method of Assigning Patients to Treatment Groups

Following confirmation of eligibility in the screening phase, patients will be randomized 2:1 to receive rucaparib or placebo. Randomization will occur by a central randomization procedure using IVRS/IWRS. The following will be included as randomization stratification factors at study entry to ensure treatment groups are balanced:

- HRD classification (tBRCA, nbHRD, or biomarker negative) by the ICTA ([Appendix A](#))
- Interval between completion of the penultimate platinum-based regimen and disease progression (6 to 12 or >12 months) by radiologic assessment
- Best response (CR [defined as complete radiologic response by RECIST] or PR [defined as partial response by RECIST and/or a GCIG CA-125 response] to platinum regimen received immediately prior to initiation of maintenance therapy. All responses require that CA-125 be <ULN.

Randomization to study treatment must occur within 8 weeks following a patient's last dose of platinum-based chemotherapy. Study treatment must be initiated within 3 days of randomization.

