### Up to 28 days prior to randomization:

- PRO collected using the FOSI-18 and EQ-5D instruments
- Physical examination by body system, including height and weight
- Vital signs (blood pressure, pulse, and temperature)
- 12-lead ECG
- Prior and concomitant medications and any surgical procedures
- Disease assessment/tumor scans: tumor assessments should consist of clinical examination and appropriate imaging techniques (including CT scans of the chest, abdomen, and pelvis with appropriate slice thickness per RECIST; other studies (magnetic resonance imaging [MRI], X-ray, positron emission tomography [PET], and ultrasound) may be performed if required. The same methods used to detect lesions at baseline are to be used to follow lesions throughout the clinical study. If a patient has known brain metastases, this disease should be evaluated at each required assessment. CT/MRI scans of the chest, abdomen, and pelvis

performed to determine the extent of disease at baseline should also be performed at each time of disease assessment, even if the scans were negative at baseline.

- ECOG performance status ([Appendix D](#))
- AE monitoring (only if related to screening procedure)

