### **9.3 Treatment Phase**

#### **9.3.1 Day 1 of Cycles 1 and 2**

The following procedures/assessments will be completed before study drug is administered:

- PRO using the FOSI-18 and EQ-5D instruments
- Physical examination
- Weight
- Vital Signs
- Concomitant medications and procedures
- ECOG performance status ([Appendix D](#))
- Hematology
- Serum chemistry (fasting is not required)

- Serum pregnancy for women of child-bearing potential (Cycle 2 only)
- CA-125 measurement (Cycle 1 only)
- Blood sample for storage (Cycle 1 only; if sample is not collected on Day 1 of Cycle 1, it should be collected as soon as possible thereafter)
- Study drug dispensation
- AE monitoring
- Plasma PK sample (prior to first dose taken that day) (Cycle 2 only; see [Section 9.5.1](#))
- Serum sample for alpha-1 acid glycoprotein (AAG) sample (Cycle 2 only)

Study drug will be dispensed to the patient in sufficient quantity to last until the next treatment cycle. Patients will ingest study drug twice daily at about the same times every day, as close to 12 hours apart as possible. Each dose of study drug should be taken with at least 8 oz (240 mL) of room temperature water. Patients may take study drug on an empty stomach or with food (with a regular meal or within 30 minutes after a regular meal). Patients will record dosing information in their electronic dosing diary.

Patients will be instructed to refrain from taking their first dose of study drug at home on the day of their clinic visits because certain assessments must be performed prior to dosing.

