### 11.2 Statistical Methods

#### 11.2.1 General Considerations

Variables registered on a continuous scale will be presented using the following descriptive statistics: N, mean, standard deviation, median, minimum and maximum. Continuous variables may also be presented using frequencies and percentages among appropriate categorizations. Categorical variables will be presented using frequencies and percentages. The Kaplan-Meier methodology will be used to summarize time-to-event variables. The number of patients with events and the number of censored patients will also be presented. The stratified logrank test will be used to compare the time-to-event distributions between the randomized treatment groups. In addition, the Cox proportional hazards model will be used to estimate the HR between the randomized treatment groups.

The primary and key secondary endpoints will be tested among the tBRCA and all HRD subgroups, and all randomized patients, using an ordered step-down multiple comparisons procedure. Investigator determined PFS (invPFS) in the tBRCA subgroup will be tested first at a one-sided 0.025 significance level. If invPFS in the tBRCA subgroup is statistically significant, then invPFS will be tested in the all HRD subgroup followed by invPFS in all randomized patients. Continuing in an ordered step-down manner, the PRO of disease symptoms utilizing the FOSI-18 DRS-P subscale will be tested at the one-sided 0.025 significance level in the tBRCA, all HRD, and all randomized patients subgroups and then for the remaining key secondary endpoints of PRO utilizing the FOSI-18 total score and OS. Once statistical significance is not achieved for one test the statistical significance will not be declared for all subsequent analyses in the ordered step-down procedure.

PFS by IRR will be evaluated as a stand-alone secondary endpoint.

All data will be used to their maximum possible extent but without any imputations for missing data.

All statistical analyses will be conducted with the SAS® System, v9.1 or higher.

Unless otherwise specified, baseline is defined as the last measurement on or prior to the first day of study drug administration.

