#### **11.2.5.2 Clinical Laboratory Evaluations**

Clinical laboratory evaluations include the continuous variables for hematology, serum chemistry, and urinalysis. The laboratory values will be presented in SI units. The on-treatment period will be defined as the time from the first dose of study drug to 28 days after the last dose of study drug. Laboratory values collected during the on-treatment period will be included in the summary tables. The laboratory values collected after the on-treatment period will only be presented in the data listings.

The summary of laboratory data will include shift tables based on CTCAE for shifts in grade from baseline to maximum, minimum and last value during the on-treatment period.

Supporting laboratory data including normal ranges and abnormal laboratory flags will be provided using by-patient listings. Separate listings will be produced for clinically significant laboratory abnormalities (i.e. those that meet Grade 3 or 4 criteria according to CTCAE).

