3 GENERAL ANALYSIS CONVENTIONS

The summary tables will be presented by randomized treatment group (rucaparib vs placebo) within the nested populations outlined in the step-down procedure in Section 3.2 and other subgroups of interest.

Quantitative variables will typically be summarized using frequencies and percentages for appropriate categorizations and may also be summarized using descriptive statistics. For variables summarized with descriptive statistics, the following will be presented: N, mean, standard deviation, median, minimum, and maximum. Categorical variables will be presented using frequencies and percentages. The Kaplan-Meier methodology will be used to summarize time-to-event variables. If estimable, the 25th, 50th (median), and 75th percentiles will be presented along with the Kaplan-Meier estimates of event rates at 6-month intervals. The number of patients with events and the number of censored patients will also be presented. The stratified log rank test will be used to compare the PFS distributions between the randomized treatment groups. In addition, the Cox proportional hazards model will be used to estimate the hazard ratio between the randomized treatment groups. Months will be calculated as number of days divided by 30.4375.

All data will be used to their maximum possible extent, but without any imputations for missing data.

Unless otherwise indicated, baseline is defined as the last measurement on or prior to randomization.

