12.2 Clinical Laboratory Evaluations

Clinical laboratory evaluations include the continuous variables for hematology, serum chemistry, and urinalysis. The laboratory values will be presented in SI units. The on-treatment period will be defined as the time from randomization to 28 days after the last dose of study drug. Laboratory values collected during the on-treatment period will be included in the summary tables. The laboratory values collected after the on-treatment period will only be presented in the data listings.

The summary of laboratory data will include descriptive statistics (N, mean, SD, minimum, median, and maximum) of the maximum, minimum, and last value during the on-treatment period. Summaries using descriptive statistics of the change from baseline to the maximum, minimum, and last value during the on-treatment period will also be given.

Summary tables from baseline to the maximum on-treatment toxicity grade (CTCAE Version 4.03) for each lab parameter will be summarized. In addition, the number and percent of patients who has at least one worsening in toxicity grade on-treatment compared to baseline toxicity grade will be summarized by treatment group.

Laboratory data including normal ranges and flagged abnormal laboratory findings will be provided using by-patient listings.

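### The SAP anchors baseline and the on-treatment window at randomization, the protocol at first dose; for patients dosed on a later day, pre-dose Day 1 values can count as worsening

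*SAP*

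**What the plan says.** **Baseline.** SAP section 3: "baseline is defined as the last measurement on or prior to randomization". Protocol 11.2.1: "baseline is defined as the last measurement on or prior to the first day of study drug administration". Both are defaults that give way to a stated exception. Neither SAP 10.2.1 and 10.2.2 (FOSI-18) nor SAP 12.2 (laboratory) states one.

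**On-treatment period.** SAP 12.2: "The on-treatment period will be defined as the time from randomization to 28 days after the last dose of study drug". SAP 12.3 does the same for vital signs. Protocol 11.2.5.2: "The on-treatment period will be defined as the time from the first dose of study drug", and 11.2.5.3 agrees for vital signs.

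**Timing.** Protocol 7.2: "Study treatment must be initiated within 3 days of randomization". FOSI-18 is taken at screening, up to 28 days before randomization (protocol 9.2: "PRO collected using the FOSI-18 and EQ-5D instruments"). It is taken again on Cycle 1 Day 1 (protocol 9.3.1: "PRO using the FOSI-18 and EQ-5D instruments"), under the instruction "The following procedures/assessments will be completed before study drug is administered". Hematology, chemistry, vital signs and CA-125 are on the same Day 1 list.

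**Endpoints.** SAP 10.2.1 and 10.2.2 time worsening (4 points on DRS-P, 8 on the total score) from randomization. They do not require the triggering assessment to follow a dose. A patient with no baseline FOSI-18 is censored at randomization. SAP 11.2 adds a supportive analysis that fills a missing FOSI-18 baseline from the assessment nearest randomization, up to Cycle 2 Day 1.

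**The concern.** Three days sounds too short to matter, but it is only the gap that triggers the rule. Once Day 1 falls after the randomization date, the SAP baseline moves back to the screening visit. The Day 1 score, taken before any drug, then becomes the first post-baseline score. A chance fall of 4 points between two untreated assessments would be a DRS-P event within days of randomization.

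DRS-P is listed first among the secondary variables in the step-down (SAP 9.2), ahead of the FOSI-18 total score and final OS. One failed test ends all later claims (SAP 3.3). Events that carry no treatment information pull the hazard ratio towards 1.

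For laboratory data, SAP 12.2 counts any on-treatment grade worse than the baseline grade. A shift between screening and a pre-dose Day 1 sample could therefore be tabulated as on-treatment worsening.

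**Working it through.** **1. Timeline under each rule** (reading the SAP's rule by calendar date)

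| First dose | SAP baseline FOSI-18 | Protocol baseline FOSI-18 | Pre-dose Day 1 score under the SAP |
|---|---|---|---|
| Randomization day | Day 1 score | Day 1 score | Baseline |
| 1 to 3 days later | Screening score | Day 1 score | Post-baseline; can be an event on study day 2 to 4 |

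Oldest possible SAP baseline relative to Day 1: 28 + 3 = 31 days. Under the protocol rule no pre-dose score can be an event, because the last one is the baseline.

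In the second row, a patient with a Day 1 score but no screening score has no SAP baseline and is censored at randomization in the main analysis. The SAP 11.2 imputation rescues this patient in a supportive analysis only. It does nothing for a patient who has a screening score.

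**2. Laboratory data and vital signs.** In the second row, Day 1 pre-dose values fall after randomization and so lie inside the SAP's on-treatment window. They feed the maximum, minimum and last-value summaries and, for laboratory data, the grade-worsening count. Changing the baseline definition alone would leave them in that window. SAP 12.1 starts treatment-emergent adverse events at first dose, so the SAP's own safety windows differ.

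**3. Chance of a pre-dose DRS-P event in an affected patient.** The documents give no variability for FOSI-18, so this is assumed. With mean change 0 and change SD s, p = Φ(−4/s):

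- s = 2: Φ(−2.00) = 2%
- s = 3: Φ(−1.33) = 9%
- s = 4: Φ(−1.00) = 16%

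For orientation, a score SD of 5 with test-retest correlation 0.8 gives s = 5 × √(2 × 0.2) = 3.16 and p = 10.3%. For the total score, SD 10 and correlation 0.8 give s = 6.32 and Φ(−8/6.32) = 10.3%.

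**4. Dilution of the DRS-P hazard ratio.** Assumed: true HR 0.65, exponential times, placebo median 8 months, 2:1 allocation, uniform censoring from 3 to 12 months.

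- Probability of an ordinary event = 1 − (e^(−3λ) − e^(−12λ))/(9λ). Placebo, λ = ln 2/8 = 0.0866: 46.5%. Rucaparib, λ = 0.65 × 0.0866 = 0.0563: 33.8%. Weighted 2:1: 38.0%.
- If a fraction f of all patients has a pre-dose event (f = share affected × p), the pre-dose share of events is g = f/(f + (1 − f) × 0.380).
- Observed HR ≈ 0.65^(1 − g).

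Example, s = 3 and all affected: f = 0.091, g = 0.091/0.436 = 0.209, HR ≈ 0.65^0.791 = 0.71.

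| Change SD | 20% affected | 50% affected | All affected |
|---|---|---|---|
| 2 | 0.65 | 0.66 | 0.67 |
| 3 | 0.66 | 0.68 | 0.71 |
| 4 | 0.67 | 0.70 | 0.75 |

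Simulation of the same model agrees to within about 0.01.

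**5. Power, s = 3.** Simulated power at one-sided 0.025 with 540 patients is about 86% with no pre-dose events, 83% with 20% affected and 75% with all affected. The first DRS-P test, however, is in tBRCA, with 180 to 200 patients. Scaling z by √(180/540) = 0.577:

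- No pre-dose events: (1.96 + 1.08) × 0.577 − 1.96 = −0.20, about 42% (about 45% at 200 patients)
- 20% affected: (1.96 + 0.95) × 0.577 − 1.96 = −0.28, about 39%
- All affected: (1.96 + 0.67) × 0.577 − 1.96 = −0.44, about 33%

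**The case against.** A reader might infer that the Day 1 FOSI-18 is always post-baseline under the SAP. It is not: a patient dosed on the randomization day keeps it as baseline. The documents do not say how many start later, and the number could be small.

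A reader might also infer bias in favour of rucaparib. The documents do not support that. The trial is double-blind and these events precede any drug, so they are expected equally in both arms. The effect is conservative and does not inflate type I error.

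A third inference would be a large loss of power, for example from 86% to 61% (SD 4, all patients affected, n = 540). That is a ceiling on assumed inputs and describes the ITT test. In tBRCA, which is tested first, power under the same assumptions is below one half even without this problem, so most of the risk of stopping there has another source.

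A baseline at randomization also matches the endpoint's time origin and is a recognised intention-to-treat convention. The laboratory and vital-sign tables are descriptive. The SAP was written to the original protocol and Amendments 1 to 3, while the protocol supplied reflects Amendment 5, so the wording the SAP worked from cannot be seen. According to the protocol, the primary analysis was unblinded in 2017 and PRO collection is no longer required.

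All of this limits the size and timing of the point. It does not reconcile the two definitions, and no FOSI-18 or laboratory section of the SAP overrides the default. Keeping randomization as the time origin does not require a screening value as baseline when a later pre-dose value exists.

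**Conclusion.** The conflict between SAP 3, 12.2 and 12.3 and protocol 11.2.1, 11.2.5.2 and 11.2.5.3 is certain from the text, and nothing in the documents resolves it. Its consequence is confined to patients first dosed 1 to 3 days after randomization. For them an untreated Day 1 score can be a FOSI-18 event, and untreated laboratory values and vital signs are summarized as on-treatment. Day 1 EQ-5D and CA-125 values shift from baseline to post-baseline in the same way.

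The expected harm is noise that weakens the FOSI-18 comparisons in both arms. Primary invPFS does not use these scores, and adverse-event tables start at first dose. The size cannot be fixed from the documents. For a true hazard ratio of 0.65 it runs from almost nothing (0.65 observed at SD 2 with 20% affected) to 0.75 (SD 4, all affected), with 0.66 to 0.67 a fair reading for 20% affected at SD 3 to 4. These figures rest on the assumed SD, hazard ratio, median and censoring. The point is worth correcting because the remedy is simple and the present rule adds nothing, but it does not threaten the trial's main conclusion.

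**What to change.** 1. In SAP section 3, define baseline as the last measurement before the first dose of study drug. For patients never dosed, use the last measurement on or before randomization. Keep randomization as the time origin for the FOSI-18 endpoints.
2. In SAP 12.2 and 12.3, start the on-treatment period at first dose, as the protocol does and as SAP 12.1 does for adverse events. The safety population contains only dosed patients, so a first-dose date always exists. Both changes are needed.
3. If results are already unblinded, leave the reported analysis as it stands. Add the FOSI-18 analysis under the protocol baseline as a labelled sensitivity analysis, with the number of patients first dosed after the randomization day and the number of FOSI-18 events triggered by a pre-dose score. Those two counts would replace the assumptions used here.

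Cost: SAP wording and a derivation change. No new data are needed.

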3.1 Populations Definitions

Intent-to-Treat Population: The intent-to-treat (ITT) population will consist of all randomized patients.

Safety Population: The safety population will consist of all patients who received at least one dose of protocol-specified treatment.

In addition to the population definitions above, further analysis subgroups within the ITT population based on tumor HRD status by the CTA are outlined in Section 3.2 below.

3.2 Definition of HRD Subgroups

The CTA is a tumor tissue-based next generation sequencing (NGS) test that has been developed in collaboration with Foundation Medicine, Inc. (FMI). Tumors with potential deficiency in homologous recombination repair (HRR) may be identified by a gene mutation analysis approach or using a phenotypic genomic instability indicator such as loss of heterozygosity (LOH). The FMI CTA test is capable of both types of analyses, i.e., it can identify gene mutations for the purpose of classifying patients into 1 of 3 molecularly defined HRD subgroups for stratification at randomization (i.e., tBRCA, nbHRD, or biomarker negative as described in Appendix A), and can also assess the percentage of the tumor genome with LOH in order to classify patients as tBRCA, non-tBRCA LOH+, non-tBRCA LOH-, or non-tBRCA LOH unknown.

Clovis is blinded to treatment assignment for the efficacy data and also blinded to the percent genomic LOH results from ARIEL3, and thus no results from ARIEL3 were used to inform the pre-specification of the LOH cut-off used for HRD determination.

The purpose of the ARIEL2 study has always been to generate rucaparib efficacy data to identify the optimal % LOH cut-off for prospective testing in study ARIEL3. ARIEL2 Part 1 is a Phase 2, open-label study of rucaparib in patients with platinum-sensitive, relapsed, high-grade epithelial ovarian, fallopian tube, or primary peritoneal cancer.

The 14% LOH cut-off prospectively tested in ARIEL2 Part 1 was based on analysis of the public TCGA dataset in high-grade serous ovarian tumors. In this dataset, clinical outcome data were only available for platinum-based therapy and not for PARP inhibitor therapy. Therefore, platinum sensitivity was used as a surrogate of rucaparib sensitivity. This analysis of the TCGA dataset demonstrated that 14% was the LOH cut-off that best differentiated overall survival outcome associated with platinum-based therapy. Therefore 14% was used as the pre-specified LOH cut-off to distinguish between the LOH-high and LOH-low populations in ARIEL2 Part 1 and to test the hypothesis that LOH-high tumors would be more sensitive to rucaparib than LOH-low tumors. This was documented in a Clovis internal memo signed on February 18, 2014.

While the 14% pre-specified LOH cut-off determined from TCGA platinum data significantly discriminated patient benefit in LOH-high and LOH-low tumors, initial analysis of ARIEL2 Part 1 suggested that a range of potential LOH cut-offs (16-18%) could potentially better identify tumors that were sensitive to rucaparib, based on efficacy endpoints of investigator assessed confirmed response rate by RECIST v1.1. or investigator assessed Progression-Free Survival (invPFS). The LOH cut-off of 18% was pre-specified for ARIEL2 Part 2 because it enrolled only fourth or fifth line patients, whose tumors may have accumulated more genomic scars and therefore have higher genomic LOH (Clovis internal memo signed on August 21, 2015).

The pre-specified LOH cut-off of 16% for prospective testing of ARIEL3 was selected following an analysis of mature clinical data from ARIEL2 Part 1, which enrolled platinum-sensitive patients similar to ARIEL3. Based on an analysis of invPFS for the subgroup of non-tBRCA patients in ARIEL2 Part 1, it was found that the greatest separation in PFS distribution between LOH-high vs LOH-low to be optimal using the 16% LOH cut-off (HR=0.455, p<0.0001). The pre-specification of 16% LOH cut-off for prospective testing in ARIEL3

Patients with a percent genomic $LOH \ge 16\%$ will be classified as LOH high (LOH+). Therefore the HRD defined nested populations used in the step-down procedure is as follows:

- 1. **tBRCA:** Patients with a tBRCA mutation per the CTA.
- 2. HRD (tBRCA or non-tBRCA LOH+): Patients who are found to have a BRCA mutation per the CTA and/or to have LOH $\geq 16\%$
- 3. ITT Population

In addition, non-nested subgroups as noted below will also be explored for efficacy:

- Non-tBRCA LOH+: Patients without a tBRCA mutation and with percent of tumor genome LOH ≥ 16%
- Non-tBRCA LOH-: Patients without a tBRCA mutation and with percent of tumor genome LOH < 16%
- Non-tBRCA LOH unknown: Patients without a tBRCA mutation and with percent of tumor genome LOH unknown

